13.2. Analysis Populations

The analysis populations include the following:

Enrolled Population: The Enrolled Population is defined as all patients who have been screened and have provided written informed consent. This population will be used for the summary of patient disposition and data listings.

Efficacy Analysis Set: The Efficacy Analysis Set is defined as all patients who have been enrolled and received at least 1 dose of PT2385. This population is the primary population for analysis of efficacy.

Safety Analysis Set: The Safety Analysis Set is defined as all patients who have been enrolled and received at least 1 dose of PT2385. This population is the primary population for the summaries of demographics, baseline data, safety data, and exposure.

13.3. Statistical Analyses

All statistical summaries and analyses will be performed in SAS® Version 9.1 or higher (SAS Institute Inc., Cary, NC, USA) on a PC platform.

Results will be reported using summary tables, figures, and data listings. No inferential statistical analyses will be performed. For continuous variables, the number of patients with non missing data (n), mean, standard deviation, median, minimum, and maximum will be presented. For discrete data, the frequency and percent distribution will be presented. Unless otherwise indicated, percentages will be calculated based upon the number of patients in the Safety Analysis Set as the denominator. Graphical methods will be used, as appropriate, to illustrate study endpoints.

Summaries will be provided for the total number of patients in the population of interest and for selected variables, and subsets of patients in the population of interest.

Data recorded on the electronic case report forms and any derived data will be presented by patient in data listings.

13.3.1. Handling of Missing, Unused, or Spurious Data

The handling of dropouts and missing disease status assessments for the efficacy variables is described in their definitions. Missing data will not be estimated or carried forward for any of the other summaries.

If only a partial date is available and is required for a calculation of whether a medication is concomitant or an AE is treatment emergent, the start and stop dates will be imputed according to a predefined standard. Any partial dates will be displayed in data listings without imputation of missing days and/or months (e.g., MAR2011, 2009). No other imputation of missing data will be performed.

13.3.2. Patient Characteristics and Patient Disposition

Demographics (including gender, age, race, and ethnicity), disease characteristics, and other baseline data (e.g., medical history, concomitant medications) will be summarized using descriptive statistics. The number of patients who enter, who complete treatment, who complete long-term follow-up, who withdraw from treatment prematurely (along with the reason), and who withdraw from the long-term follow-up prematurely (along with the reason) will be tabulated.

13.3.3. Exposure

All study drug administration data will be summarized for the Safety Analysis Set. The duration of PT2385 exposure in weeks, defined as (date of administration of last dose minus date of administration of first dose of PT2385 plus 1) divided by 7 and the total amount of PT2385 administered will be summarized.

13.3.4. Efficacy Analyses

The primary summaries of all response data will be based on the Efficacy Analysis Set.

Response of ccRCC tumors will be measured by contrast enhanced computerized tomography (CT) or magnetic resonance image (MRI) scan and assessed according to RECIST 1.1, modified to follow ccRCC tumors only.

Response assessments of ccRCC CR and PR should be confirmed by a second assessment. Where confirmed responses are required, the date of the first assessment will be used in all analyses. In the case that the confirmation assessment is not available, the assessment at the next scheduled time point will be used for confirmation. If there are no assessments, the response will be taken to be unconfirmed and a non response.

The ccRCC ORR is defined as the proportion of patients for whom the best confirmed ccRCC response is CR or PR, determined by RECIST 1.1. Estimates of the ccRCC ORR along with the associated 90% and 95% exact binomial confidence intervals (Clopper Pearson) will be provided. The binomial probability that the observed ccRCC ORR is > 0.15 will be calculated. Best confirmed ccRCC response will be summarized.

The ccRCC PFS is defined the interval from the start of study treatment until the earlier of the first documentation of ccRCC disease progression determined by RECIST 1.1 or death from any cause, whichever occurs first. Renal cell carcinoma PFS will be right censored for patients who meet one of the following conditions: 1) no post baseline disease assessments, 2) non protocol systemic anticancer treatment started before documentation of disease progression or death, 3) surgery that is considered to affect response before documentation of disease assessment visit, 5) alive and does not have documentation of disease progression before a data analysis cutoff date. The Kaplan-Meier (KM) method will be used to estimate the distribution of ccRCC PFS. Quartiles including the median will be estimated by KM method along with their 95% confidence intervals. A figure showing the estimated ccRCC PFS distribution will be provided. KM cumulative estimators along with the associated 95% CIs will be provided for ccRCC PFS rates at 26, 39 and 52 weeks. Duration of follow up for ccRCC PFS will be summarized according to the KM estimate of potential follow up also termed "reverse Kaplan-Meier."

The ccRCC DOR will be calculated for patients who achieve a ccRCC CR or PR. For such patients, the ccRCC DOR is defined as the interval from first documentation of response, as determined by RECIST 1.1, to the earlier of the first documentation of disease progression or death from any cause. Dates of progression and censoring will be determined as described for the analysis of ccRCC PFS. Kaplan-Meier methods will be used to estimate the distribution of ccRCC DOR. Quartiles including the median will be estimated by KM method along with their 95% confidence intervals. KM cumulative estimators along with the associated 95% CIs will be provided for ccRCC DOR rates at 26, 39 and 52 weeks. These estimates will be used as estimates of durable response.

The ccRCC TTR will be calculated for patients who achieve a ccRCC CR or PR. Renal cell carcinoma TTR is defined as the interval from the start of study treatment to the first documentation of a ccRCC response of PR or better, as determined by RECIST 1.1.

The maximum percent decrease in ccRCC total tumor burden will be displayed using waterfall plots.

Summaries of the response endpoints will also be provided for subgroups of the Efficacy Analysis Set as follows: Subgroups will be defined according to blood level of PT2385 based on the PK assessments and duration of PT2385 treatment. The analyses of ccRCC ORR, ccRCC PFS, ccRCC best confirmed response, ccRCC DOR, and ccRCC TTR will be performed in each of these subgroups.

The ORR, PFS, best confirmed response, DOR, and TTR will be summarized for the nonccRCC tumors associated with VHL disease based on the subgroups of patients in the Efficacy Analysis Set who have the particular type of tumor. The determination of best response and date of progression will be determined by modifying RECIST 1.1 criteria to assess tumors in individual organ systems independently (e.g., VHL disease-associated solid tumors in the pancreas or adrenal gland, or hemangioblastomas or retinal angiomas).

The determination of response and progression will be made by the local investigators. The investigator assessments will be used for decisions regarding treatment for individual patients and by the DMC for approval to open Stage 2 of the study. The response outcomes will also be reviewed and determined by an Independent Review Committee (IRC). For the primary analysis of ORR, the determination of response will be based on independent radiologic assessment conducted by the IRC. Both the investigators' and the IRC's assessments will be used for the summaries and analyses of efficacy.

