10. ASSESSMENT OF EFFICACY

10.1. Efficacy Parameters

Primary endpoint: Best confirmed response in VHL disease-associated ccRCC tumors, defined as the proportion of the best confirmed response of CR or PR (as assessed by the Independent Review Committee (IRC)) as determined by RECIST 1.1, modified to follow ccRCC tumors only. ORR is defined as the proportion of patients with a best confirmed response of CR or PR.

Secondary endpoints:

- Progression-free survival (PFS) in VHL disease-associated ccRCC tumors, defined as the interval from the start of study treatment until the earlier of the first documentation of disease progression determined by RECIST 1.1 or death from any cause, and calculated for patients with a best confirmed response of CR or PR
- Duration of response (DOR) in VHL disease-associated ccRCC tumors, defined as the interval from the first documentation of response, as determined by RECIST 1.1, to the earlier of the first documentation of disease progression or death from any cause, and calculated for the patients with a best confirmed response of CR or PR
- Time to response (TTR) in VHL disease-associated ccRCC tumors, defined as the interval from the start of study treatment to the first documentation of a response, as determined by RECIST 1.1, and calculated for patients with a best confirmed response of CR or PR
- Best confirmed response, PFS, DOR, and TTR for non-ccRCC tumors associated with VHL disease in different organ systems, by modifying RECIST 1.1 criteria to assess tumors in individual organ systems (Appendix 4)

Exploratory endpoint:

• Changes in PD markers (e.g., serum EPO)

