13. STATISTICS

This section describes the statistical methodology to be used in the analysis of protocol endpoints. These methods will be documented in a formal statistical analysis plan (SAP) detailing the analyses to be performed, which will be developed before the final database lock. The SAP will serve as the final arbiter of all statistical analyses. The SAP will describe the analysis of all safety, efficacy, PK, and PD response variables. Any changes to the methodology described in the final approved SAP will be presented and discussed in the clinical study report.

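### Condition 1 of the ccRCC PFS censoring rule (Section 13.3.4), as written, censors a death before the first scan, and the PFS population is stated in two ways

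*Combined protocol and SAP*

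**What the plan says.** Section 13.3.4 runs ccRCC PFS from the start of treatment to "disease progression determined by RECIST 1.1 or death from any cause, whichever occurs first". The next sentence says that PFS is "right censored for patients who meet one of the following conditions: 1) no post baseline disease assessments". Condition 2 censors for non-protocol systemic anticancer treatment begun before progression or death. Condition 3 begins "surgery that is considered to affect response before documentation of disease"; the rest of it and most of condition 4 are lost in the supplied text. Condition 5 applies to a patient who is "alive and does not have documentation of disease progression before a data analysis cutoff date".

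No other rule fills the gap. On missing data, Section 13.3.1 says: "The handling of dropouts and missing disease status assessments for the efficacy variables is described in their definitions". For DOR, Section 13.3.4 says: "Dates of progression and censoring will be determined as described for the analysis of ccRCC PFS". Section 13 announces a formal SAP: "The SAP will serve as the final arbiter of all statistical analyses". That SAP is not part of the text reviewed here.

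On who is analysed, Section 10.1 ends its PFS definition with "or death from any cause, and calculated for patients with a best confirmed response of CR or PR", and the Synopsis does the same. Section 10.1.1 says PFS is determined for all patients and keeps the responder restriction for DOR and TTR. Section 13.3.4 puts no responder restriction on PFS and bases its primary response summaries on the Efficacy Analysis Set.

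**The concern.** A patient who dies before any follow-up scan meets the event definition and also meets condition 1. The instruction attached to condition 1 is to censor. A programmer who follows the text would remove from the curve exactly the deaths that the definition was written to count.

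The population conflict matters separately. Responder-only PFS leaves out everyone who progresses or dies without responding, so it answers a different question and reads higher. The study has no comparator against which either effect could cancel.

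Surgery raises a related but weaker question. Kaplan-Meier assumes that censoring is unrelated to prognosis. Section 4.1.1 ties renal surgery to the largest tumor reaching about 3 cm, and Section 7.2.1 admits no solid ccRCC tumor above 3.0 cm. Operated patients may therefore be those closest to progression.

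**Working it through.** The documents give no PFS rate, event count or precision target, so there is no plan figure to reproduce. The check is textual, with arithmetic for scale.

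**1. Does condition 1 override the event definition?**
- Meeting one condition is enough for censoring, so no other item in the list can take a patient back out.
- Condition 5 is limited to living patients and condition 2 refers to death. Condition 1 does neither.
- The list is not confined to patients without an observed event. Condition 2 censors a patient even if progression or death follows later.
- The first scan falls in the 7 days before the Week 13 visit (Section 10.1.1). Any death before it meets condition 1.

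**2. Size with n = 50 (Section 6.2).** Let d be deaths before the first scan and e later progressions by week 52. Assume that all progressions follow the deaths and that there is no other censoring. Death as an event gives (50 − d − e)/50. Death censored gives (50 − d − e)/(50 − d). The values of d and e are assumptions.

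| d | e | Death as event | Death censored | Difference |
|---|---|---|---|---|
| 1 | 0 | 49/50 = 0.980 | 49/49 = 1.000 | 2.0 points |
| 1 | 5 | 44/50 = 0.880 | 44/49 = 0.898 | 1.8 points |
| 1 | 10 | 39/50 = 0.780 | 39/49 = 0.796 | 1.6 points |
| 2 | 5 | 43/50 = 0.860 | 43/48 = 0.896 | 3.6 points |
| 3 | 10 | 37/50 = 0.740 | 37/47 = 0.787 | 4.7 points |
| 3 | 0 | 47/50 = 0.940 | 47/47 = 1.000 | 6.0 points |

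In the third row the binomial standard error is √(0.78 × 0.22/50) = 0.059, so one death moves the estimate by 0.016/0.059, about 0.3 of a standard error.

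**3. Reach.** A confirmed responder has had a post-baseline scan, so condition 1 cannot touch DOR. For the same reason its effect on PFS would be zero if PFS covered responders only. At the smallest number of responders that rejects the null hypothesis, 13 of 50 (Section 13.1), responder-only PFS would leave out 50 − 13 = 37 patients.

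**4. Surgery (illustrative).** The documents give no surgery rate and no PFS rate. Suppose the hazard is constant and a fraction f of progressions is replaced by surgery just beforehand and censored. Kaplan-Meier then estimates S^(1−f) instead of S.
- True 0.81: f = 0 gives 0.81, f = 0.10 gives 0.827, f = 0.25 gives 0.854, f = 0.50 gives 0.900.
- True 0.70: from 0.70 at f = 0 to 0.837 at f = 0.50.
- True 0.90: from 0.90 at f = 0 to 0.949 at f = 0.50.

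If surgery is unrelated to growth, the planned analysis has no bias, and counting surgery as an event reads too low. With 10% unrelated surgery by week 52, a true 0.822 would read 0.822 × 0.90 = 0.740.

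**The case against.** The best counter-argument is that the event definition governs and censoring applies only where no event was seen. Conditions 2 and 5 mention death or being alive, which suggests that the authors meant deaths to count. That is good evidence of intent, and the fault is accordingly one of wording. It does not rescue the text, because condition 2 already censors patients who may have a later event.

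A second argument is that part of the list is lost. That bars any conclusion about conditions 3 and 4, but condition 1 is intact and is sufficient on its own.

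On surgery most of the opposing case stands. The clause is damaged, and what survives covers only surgery considered to affect response. No censoring date for it can be read. Section 7.2.2 excludes patients with an immediate need for tumor surgery, and a tumor just under 3 cm can reach 3 cm without RECIST progression. A reader might infer that surgery censoring is shown to inflate PFS and DOR, or that no check of it is planned anywhere. The documents support neither: informativeness is plausible but not shown, and the formal SAP may contain the check.

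**Conclusion.** Condition 1 is wrong as written, and the fault is minor. It contradicts the event definition and would raise PFS by about 2 points per death before the first scan, given 50 patients and PFS estimated in all of them. Such deaths should be few, since any history of metastatic disease is an exclusion. PFS is a secondary endpoint summarized descriptively, and DOR and the ORR test are unaffected. It would go too far to say that the sponsor intends to drop early deaths from PFS; the text is merely missing a qualifier.

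The conflict over the PFS population is also real and changes what is estimated.

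The surgery question supports no more than an optional supplementary analysis. The size of any effect cannot be derived from the documents. It can be given only as a range that rests on assumptions and includes zero.

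**What to change.** - **Condition 1.** Reword to *no post-baseline disease assessment and not known to have died*, so that a death before the first scan is a PFS event. This costs a few words. A late death in a patient who left before any scan should follow the plan's rule for missed visits; that rule cannot be checked here because most of condition 4 is lost.
- **Population.** State that ccRCC PFS is estimated in the full Efficacy Analysis Set, and bring the Synopsis and Section 10.1 into line with Sections 10.1.1 and 13.3.4. This is a text change only.
- **Optional, unless the SAP already has it.** Keep the planned PFS and DOR analyses. Beside them show one supplementary Kaplan-Meier analysis that counts the surgery named in condition 3 as an event, with that same trigger and no broader one. Surgical history is already collected in long-term follow-up (Section 6.1 and Appendix 1, note 16). Whether the dates are precise enough cannot be checked, because the CRF was not supplied. The cost is one more set of outputs, and a figure that understates progression-free time if surgery is unrelated to growth. The two results should therefore be read together.

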be summarized. Estimates of the ccRCC ORR along with the associated 90% and 95% exact binomial confidence intervals (Clopper-Pearson method) will be provided. The binomial probability that the observed ccRCC ORR is > 0.15 will be calculated. Best confirmed response will be summarized. The ccRCC TTR will be calculated for patients who achieve a ccRCC CR or PR. The maximum percent decrease in ccRCC tumor burden will be displayed using waterfall plots. The ccRCC PFS and ccRCC DOR will be summarized descriptively using the Kaplan-Meier method. The median and quartiles of ccRCC PFS and ccRCC DOR will be calculated along with 90% and 95% confidence intervals.

Summaries of the response endpoints will also be provided for subgroups of the Efficacy Analysis Set as follows: Subgroups will be defined based on site of primary tumors other than ccRCC at screening, blood level of PT2385 based on the PK assessments, and duration of PT2385 treatment. The analyses of ORR, PFS, best confirmed response, and DOR will be performed in each of these subgroups.

The ORR, PFS, DOR, and TTR will be summarized for the individual types of non-ccRCC tumors using modified RECIST 1.1 criteria. The modification to RECIST 1.1 is to evaluate different organ system tumors independently (e.g., VHL disease-associated solid tumors in the pancreas, adrenal gland, or hemangioblastomas or retinal angiomas).

The determination of response and progression will be made by the local investigators. The investigator assessments will be used for decisions regarding treatment for individual patients and by the DMC for approval to open Stage 2 of the study. The response outcomes will also be reviewed and determined by an Independent Review Committee (IRC). For the primary analysis of ORR, the determination of response will be based on independent radiologic assessment conducted by the IRC. Both the investigators' and the IRC's assessments will be used for the summaries and analyses of efficacy.

Safety Assessments

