6. INVESTIGATIONAL PLAN

6.1. Overall Study Design

This open-label Phase 2 study will evaluate the efficacy, safety, PK, and PD of PT2385 in patients with VHL disease who have at least 1 measurable VHL disease-associated ccRCC tumor (as defined by RECIST 1.1). PT2385 will be administered orally at a dosage of 800 mg twice daily. Treatment will be continuous; the drug will be administered twice daily every day. Patients will be entered in the study after meeting all inclusion criteria and no exclusion criteria. This study will be conducted with a 2-stage design, which allows for an early assessment of futility. A response will be defined as either a PR or CR occurring at any time after initiation of treatment, based on assessment of ccRCC tumors. All responses must be confirmed after the initial response is documented. Changes in VHL disease-associated non-ccRCC tumors will also be evaluated independently by modifying RECIST 1.1 criteria to assess tumors in individual organ systems independently rather than collectively.

Twenty-five patients will be enrolled during the first stage. A Data Monitoring Committee (DMC) will perform the safety review for the first 6 patients and the futility analysis for Stage 1 of the study. The DMC will review safety and any treatment-limiting toxicities to confirm whether the study should continue to enroll or if modifications to the protocol are needed. The DMC will review the response data from the first 25 patients to determine if at least 3 patients have a confirmed PR or better in ccRCC tumors and that the threshold for opening Stage 2 has been met. Treatment-limiting toxicities will be assessed according to Section 6.4. Study termination criteria are presented in Section 6.5.

In the second stage of the study, 25 additional patients will be enrolled, to a maximum accrual of 50 patients.

Patients will undergo clinical and laboratory evaluations every 2 weeks for the first 4 weeks and then every 4 weeks (i.e., 28 days) according to the Schedule of Events. Patients will be evaluated radiologically for evidence of response or progression approximately 12 weeks after initiation of treatment and every 12 weeks thereafter while continuing in the study. Patients with evidence of stable disease or disease response, i.e., CR or PR, will continue to receive treatment in the absence of serious toxicity. Patients who demonstrate disease progression of their ccRCC tumors at any time will be withdrawn from study treatment.

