10.1.1. Response in VHL Disease-Associated ccRCC Tumors

Anti-tumor activity will be assessed by non contrast or contrast computerized tomography (CT) or magnetic resonance imaging (MRI) at baseline, within 7 days before the Week 13 visit and every 12 weeks thereafter. Patients will be imaged using the same technique at baseline and each follow up assessment.

Response assessments will be made using RECIST 1.1 (Appendix 3), modified to follow ccRCC tumors only. Best confirmed response and PFS will be determined for all patients. DOR and TTR will be determined for all patients with a best confirmed response of PR or CR. The ORR for VHL disease-associated ccRCC tumors will be determined.

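### ccRCC efficacy is to be tabulated by duration of PT2385 treatment, which progression itself cuts short, so PFS and DOR will look better with longer treatment largely by construction

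*Combined protocol and SAP*

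**What the plan says.** Section 13.3.4 (Efficacy Analyses) states: "Subgroups will be defined according to blood level of PT2385 based on the PK assessments and duration of PT2385 treatment". It then lists ccRCC ORR, PFS, best confirmed response, DOR and TTR for analysis in each subgroup. The synopsis names the same two variables, "blood level of PT2385 based on the PK assessments, and duration of PT2385 treatment", adds tumour site, and leaves out TTR. Neither place gives cut-points, a landmark or a caution on interpretation.

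The only definition of duration is in section 13.3.3 (Exposure): "date of administration of last dose minus date of administration of first dose of PT2385 plus 1", divided by 7.

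Section 6.1 (Overall Study Design) links treatment to outcome in both directions: "Patients with evidence of stable disease or disease response, i.e., CR or PR, will continue to receive treatment in the absence of serious toxicity", and "Patients who demonstrate disease progression of their ccRCC tumors at any time will be withdrawn from study treatment". Section 13.3.4 ends ccRCC PFS at ccRCC progression or death, and DOR takes its progression and censoring dates from PFS. The same section says that investigator assessments guide treatment, while the IRC's determine the primary ORR.

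Scans are due "within 7 days before the Week 13 visit and every 12 weeks thereafter". If a confirming scan is missing, "the assessment at the next scheduled time point will be used for confirmation".

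**The concern.** Treatment duration is a post-baseline variable, known only once treatment has ended, and the event that ends PFS and DOR also ends treatment. A patient can enter a long-duration group only by remaining free of investigator-assessed ccRCC progression and death for about that long. Comparing PFS or DOR across such groups largely restates how the groups were formed.

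ORR is pulled the same way less directly. A response needs a second assessment, and progression before that assessment both prevents confirmation and shortens treatment.

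The risk is one of reading. Tables produced as planned could be taken to show that staying on PT2385 longer gives more, and more durable, responses. Section 13.3.4 intends the 26-, 39- and 52-week DOR rates as estimates of durable response, which makes a by-duration version easy to over-read.

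**Working it through.** The plan states no figure for these subgroups, so there is none to reproduce. The direction follows from the rules above. The size is illustrative.

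**Inputs from the documents:** 12-weekly scans; treatment ends at ccRCC progression; PFS rates at 26, 39 and 52 weeks; 50 patients; 30% response rate (the design alternative).

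**Assumed, not in the documents:** a 52-week cut; exponential progression with median m = 48, 96 or 192 weeks, documented at the next scan; treatment stopped for other reasons independently of prognosis, exponential with median 120 weeks; scans continuing after treatment stops. Duration has no effect on progression in this model.

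**Step 1, overall PFS.** The last scan before week 52 is at week 48, so scan-documented 52-week PFS is S = 2^(−48/m) = 0.500, 0.707, 0.841. The underlying 52-week values, 2^(−52/m), are 0.472, 0.687, 0.829.

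**Step 2, longer group (at least 52 weeks), dosing stopped at the progression scan.** Nobody with progression documented by week 48 can be in this group. PFS at 26, 39 and 52 weeks is 100% for every m.

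**Step 3, the same group if dosing runs 4 weeks past the progression scan.** Patients whose progression is found at week 48 now reach week 52. The 52-week PFS becomes 2^(−48/m) ÷ 2^(−36/m) = 2^(−12/m) = 0.841, 0.917, 0.958. The 26- and 39-week rates stay at 100%.

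**Step 4, shorter group, dosing stopped promptly.** The chance of no other stop by week 52 is G = 2^(−52/120) = 0.741. Patients progression-free at 52 weeks are in the shorter group only through another stop:

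PFS at 52 weeks = S(1 − G) ÷ (1 − S·G)

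| m (weeks) | S(1 − G) | 1 − S·G | Shorter group | Overall |
|---|---|---|---|---|
| 48 | 0.130 | 0.630 | 20.6% | 50% |
| 96 | 0.183 | 0.476 | 38.5% | 71% |
| 192 | 0.218 | 0.377 | 57.8% | 84% |

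**Step 5, DOR and ORR (simulation, same model).** Response propensity is 30%, mean latency 12 or 24 weeks, confirmation 4 or 12 weeks later, and response does not depend on staying on treatment. The 26-week DOR rate is 46-89% in the shorter group against 92-99% in the longer. ORR is 11-25% against 28-30%. If responses count only when confirmed on treatment, ORR is 6-16% against 27-30%. The gap that remains when treatment has no effect on response is 36-80% of that on-treatment gap.

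**Step 6, sensitivity.** Under a different set of assumptions (median split; median progression 52, 104 or 156 weeks; other-stop median 52, 104 or 208 weeks; scans continuing or not), PFS and DOR favoured the longer group in all 18 scenarios. Shifting 30% of IRC progression dates by 12 weeks in the 104/104-week case left 52-week PFS at 0.98 against 0.48, so IRC reading does not remove the effect.

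**The case against.** The strongest case against is that little hangs on this. Section 13.3 says that no inferential analyses will be performed, no between-subgroup test is stated, and section 13 leaves detail to a formal SAP that is to be the final arbiter. That stands as a limit on consequence. It does not remove the bias, which comes from the grouping and needs no p-value, and nothing in the documents replaces the analysis.

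A reader might infer that the 100% holds without assumptions. It does not. It needs the chosen cut and prompt stopping. Section 6.1 says patients will be withdrawn at progression, section 7.2.3 says the investigator may discontinue for it, and the synopsis refers to unequivocal progression. Step 3 shows the effect of a lag: the figure softens and the direction stays.

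A reader might also infer that any ORR gradient is spurious. The documents do not support that, since patients who stop early may respond less because they were treated less. TTR is not expected to look better either: in the simulation, responses are later on average in the longer group.

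Treatment also ends for toxicity, non-ccRCC progression, long interruption or withdrawal of consent, so membership is only partly set by the outcome. The medians and stopping rates are assumed and the ranges are wide.

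**Conclusion.** The concern holds for PFS and DOR: following the plan as written gives by-duration tables whose gradient is largely built in. The direction rests on the protocol's own rules. The sizes (essentially 100%, or about 84-96% at 52 weeks with a dosing lag, in the longer group; about 21%, 38.5% and 58% in the shorter) rest on the 52-week cut, exponential times, independent other stops and continued scans. For ORR the direction is likely, but the artefact cannot be separated from a true effect of too little treatment.

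The impact is low. A reader might take this as a flaw in the main efficacy result; it is not one. The primary ORR, the rule of 13 responders in 50 and overall PFS do not use these subgroups, and no decision in the documents depends on them.

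**What to change.** Delete duration of PT2385 treatment as an efficacy subgroup variable in section 13.3.4 and the synopsis, and do not carry it into the SAP. Duration stays summarised under Exposure (section 13.3.3).

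If the question is kept, replace the tables with an analysis labelled exploratory: either on-treatment status as a time-dependent covariate, or a fixed landmark such as the week-24 scan among patients still progression-free and under follow-up. In the model above, a week-24 landmark removes the spurious gap (48 weeks later, on and off treatment are both 0.50, 0.71 and 0.84), given that stopping is independent of prognosis.

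The SAP should state two limits:

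- **Sparse data.** The expected number off treatment and progression-free at week 24 is 50 × 2^(−24/m) × (1 − 2^(−24/120)) = 4.6, 5.4 or 5.9, so about 5 of 50 (about 2 to 11 if the other-stop median is 240 or 60 weeks).
- **Off-treatment scans.** The analysis needs them, and the documents leave their existence unclear: section 6.1 has imaging "every 12 weeks thereafter while continuing in the study", while the Schedule of Events marks no tumour assessment after treatment. That is a separate point to reconcile.

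The cost is the loss of the descriptive duration tables. A landmark analysis also drops patients with events before the landmark and does not count responses already documented by then. The change can be made in the SAP, with the protocol wording aligned at the next amendment.
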